Objectives:	We aim to use a CES (cranial electrotherapy stimulation) intervention to improve emotional well-being by reducing symptoms of anxiety and depression and to assess for changes in markers of cellular health - specifically, telomere length and telomerase activity
Study Design:	Randomized, double-blinded, sham controlled trial
Study Population:	18-40 year old males, with symptoms of mild to moderate anxiety and/or depression, in the absence of a psychotic disorder
Phase:	Pilot
Study Site:	UCLA Oppenheimer Family Center for Neurobiology of Stress and Resilience
Description of Intervention:	A commercially available cranial electrotherapy stimulation device that applies an electrical current to a subject's head to treat anxiety, depression or insomnia. Electrical stimulation will be applied via ear clip electrodes at the lowest setting (0.5 Hz, 100 μ A) for 1 hour daily for eight weeks. In the sham group, the electrodes attached to the device will be inactive.
Study Duration:	24 months
Subject Participation Duration:	8-10 weeks
Estimated Time to Complete Enrollment:	20 weeks

2 INTRODUCTION: BACKGROUND INFORMATION AND SCIENTIFIC RATIONALE

2.1 Background Information

Chronic emotional distress can lead to detrimental biological outcomes, presumably via alterations in the hypothalamic pituitary adrenal axis (HPA axis), a sympathetic bias of the autonomic nervous system, and inflammatory dysregulation.¹ At the cellular level, impairment of the telomere/telomerase system may be a result of this dysregulation, given the descriptions of shorter telomeres (a marker of cellular aging), as well as increased markers of inflammation, in subjects with depression, anxiety and PTSD, compared to aged matched healthy populations.²⁻⁵ These negative cellular effects of emotional distress have not been well studied. In this study we aim to use an auricular CES intervention to improve emotional well-being by reducing symptoms of anxiety and depression and to assess for changes in markers of cellular health - specifically, telomere length and telomerase activity.

This feasibility study was initially developed to study Veterans specifically, however, due to difficulty with recruitment in the Veteran population the study inclusion criteria were adjusted to include non-Veteran eligible male subjects and appropriate modifications were made in the regulatory documents.

2.2 Rationale

Auricular CES, anxiety and depression

Auricular CES benefits centrally mediated symptoms such as anxiety, depression, insomnia and pain; however, the mechanism by which the benefit occurs is not entirely clear. Similar to auricular electro-acupuncture, auricular CES is believed to act on subcortical brain structures, including the thalamus and limbic regions. This concept is supported by several small functional neuroimaging and EEG studies.⁶⁻⁸ Neuroimaging during application of auricular CES shows alterations in resting brain networks, as well as a tendency toward widespread decreases in cortical activation.⁹ In a study of an 8 week auricular CES intervention for pain, post treatment subjects had pain reductions as well as decreased blood oxygen dependent (BOLD) response in the basal ganglia and parahippocampal gyrus compared to subject treated with a sham device.¹⁰

Several small studies have shown benefits of auricular CES on negative affect symptoms. Anxiety symptoms were reduced by at least 50% in 67% of patients with generalized anxiety disorder using auricular CES in an open label study for 6 weeks.¹¹ Other studies have shown anxiety reductions in pre-procedure dental patients¹² and fibromyalgia patients.¹³ Reduction in depression symptoms has been described in multiple reviews, with most studies only in abstract or unpublished forms, or using depression as a secondary outcome.¹⁴⁻¹⁷ Pilot evaluations of electro-acupuncture and of external trigeminal nerve stimulation,

two interventions with similar targets, have also suggested that this approach may have a benefit for depression.^{18,19} In one study of auricular CES using the same protocol proposed here, 115 patients with anxiety or anxiety and comorbid depression were studied over 5 weeks in a randomized, sham controlled trial, showing significant improvements in both anxiety and depression symptoms with high effect sizes ($d=.8$ and $d=.94$).¹⁷ Due to the complexity of overlapping negative affect symptoms that lead to impaired emotional wellbeing in Veterans, we chose in this proposal to evaluate a composite measure of emotional distress (a combined anxiety and depression score) as the primary outcome. Beyond depression and anxiety, CES has been associated with reductions in insomnia and pain, both of which are also significant problems in Veterans, likely contributing to reduced emotional well-being.^{14, 20-22} Data collected during program evaluation at a GLA affiliated (Veterans Integrated Service Network 22) VA Medical Center, use of CES in Veterans with comorbid PTSD, anxiety and depressive symptoms showed improvements in the Beck Depression Inventory, Beck Anxiety Index, and Insomnia Severity Index after a 1 week open label trial of 40-60 minutes of auricular CES per day (personal communication, [name], PsyD). While the published literature is still immature, we anticipate that CES may be a particularly useful treatment in the Veteran and non-Veteran populations given that it may target multiple symptoms causing emotional distress.

Cellular aging, anxiety, and depression

Telomeres are repeating DNA-protein complexes that cap the ends of chromosomes, protecting the DNA from damage during replication. The terminal end of the telomere shortens with successive replication as the cell ages. This aging can be accelerated in settings of stress, including symptoms of emotional distress such as anxiety and depression.¹ Reductions in telomere length have been associated with anxiety, depression, PTSD, and unhealthy lifestyles, all common conditions in OIF/OEF Veterans.²⁻⁵ Little is known about telomere length and telomerase activity in Veterans specifically, though PTSD in Veterans has been associated with telomere shortening.⁵ The mechanism through which affective symptoms and emotional stress lead to peripheral changes in the telomere/telomerase system has not been completely elucidated but is likely the result of a dysregulated hypothalamic pituitary adrenal axis, impaired anti-inflammatory pathways, and a sympathetic shift of the autonomic nervous system, all leading to greater cellular stress. It is unclear whether reductions in telomere length create a permanent "biological scar" during periods of systemic stress or whether compensatory increases in telomerase can lengthen the telomeres, as there is contradictory evidence for both situations in human studies.¹ Mind-body interventions, such as meditation, as well as pharmacological approaches, have been shown to improve telomerase levels and telomere length.^{1,23}

In this study we hypothesize that the complex chronic stressors, which include anxiety, depression, PTSD, insomnia, and chronic pain will lead to biological stress at the cellular level. This stress will have resulted in greater than normal telomere shortening and suppressed telomerase, as has been described in PTSD.²⁴ Improvement in key symptoms of emotional distress, anxiety and depression, is expected to lead to decreased biological stress, and increases in telomerase activity, possibly with improvements in telomere length, though the latter may require a longer follow up.

2.3 Potential Risks and Benefits

The study devices used are commercially available and have an excellent risk profile based on previous human clinical studies and post marketing data.

2.3.1 Potential Risks

The most common side effects of the device are dizziness, headache, and local skin irritation. Dizziness and headache most commonly occur at higher current levels but will be minimized by having the first electrical stimulation session performed at the research center to make sure the study protocol is tolerated. Subjects who cannot tolerate the study protocol will be dropped from the study. Phlebotomy has a low risk of bruising, swelling or pain at the site, and a very low risk of infection.

The collection of data contains the inherent risk of loss of privacy. This risk will be minimized by adequate training of all study staff according to institutional guidelines, use of unique subject identifiers, and by keeping data in password protected computer databases and/or locked cabinets. An informed consent document was approved by the local Institutional Review Boards at UCLA and a recruitment waiver was obtained from the IRB at the Greater Los Angeles VA. All subjects will read and document understanding of the consent form prior to enrolling in the study.

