4.4 Randomization and Blinding

This is a randomized, double-blinded, sham controlled study. The active and sham devices are identical in appearance and will only differ by the labeling of a unique serial number. In the sham devices, the electrodes attached to the device will be inactive. The subjects will be instructed that the device is set to a low level so that the current is not detectable but still effective. The current will not be detectable in both active and sham devices in order for adequate blinding to occur.

To ensure that the allocation of subjects to treatment is properly concealed, the PI and research personnel will not know which devices are active or sham. The sponsor will provide the code to determine which devices are active and which are sham. Code will be in a sealed envelope that will not be opened until the end of data collection.

Schematic of Study Design

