5.5 Treatment Assignment Procedures

Stratified random sampling will be performed using SAS Proc Plan to generating random sequences and dispensing one of the Alpha-Stim AID kits provided by the sponsor (50% of kits active, 50% sham) and coded with unique serial numbers.

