6.2.1 Dosage

The dose selection (device frequency of 0.5 Hz and 100 μ A) is based on previous positive studies of the device for anxiety, depression, and insomnia. The dose selected is not detectable by the subject, so that adequate blinding can occur.

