7.2 Enrollment/Baseline Screening (Visit 1)

This visit will occur at the Oppenheimer Family Center for Neurobiology of Stress. It will take about 3 hours to complete the screening and device training process. The research team will verify OEF/OIF Veteran status (i.e. DD 214) before study enrollment if the subject identifies as a Veteran. The potential subjects will first review and sign ICF and HIPAA Authorization with either the RN, FNP, or MD. All are certified to obtain informed consent (nursing or physician license). Subjects will be identified by the PI, [name], as possibly eligible after the clinic visit and the study questionnaires have been completed and scored. Medical history will be reviewed and a physical will be performed as well. The assessment questionnaires include:

- A standardized psychiatric evaluation (MINI)
- Hospital Anxiety and Depression Scale (HADS)
- Mental Health Continuum Short Form (MHC-SF)
- Patient Reported Outcomes Measurement Information System (PROMIS-29)
- Positive and Negative Affect Schedule Short Form (PANAS-SF)
- Connor-Davidson Resilience Scale (CD-RISC)
- Perceived Stress Scale (PSS)
- Patient Health Questionnaire (PHQ)

-
- Columbia-Suicide Severity Rating Scale (C-SSRS) Self Report Screener - Recent

We will use the HADS to assess symptom severity defined as normal range (0-7), mild (8-10), moderate (11-14) or severe (15-20). Subjects with impaired emotional wellbeing as defined as a minimum combined HADS score of 14 will be included. Subjects who score >15 will be excluded in the study and will be given referrals to their personal provider or community mental health resources. (See “Reporting Suicidal Ideation” Section 5.4)

Subjects who express interest in participating and meet the inclusion criteria will be trained to use the CES device. They will be instructed that the device is set to a low level that should not be detectable. Subjects will have their first 1 hour treatment at OCNS (commencing Week 1 of the study). Subjects who tolerate the device treatment will then have blood drawn for baseline biological measures. They will be informed that this is a randomized controlled trial and they may or may not have an active device kit. Subjects will be sent home with a device, instructions for daily treatment, and a patient diary to track usage and side effects if applicable.

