9.2 Time Period and Frequency for Event Assessment and Follow-Up

All AEs reported by subjects or observed during the study will be recorded. All AEs shall be recorded in subject's file regardless of perceived causality. AEs will be assessed from the first device treatment (screening visit) to the last device treatment. AE form will be collected during each study visit at OCNS.

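### Men who cannot tolerate the first device session are dropped with no later HADS; if the kit is already allocated, as seems likely, this is a post-randomisation exclusion that can differ by arm

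*Combined protocol and SAP*

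**What the plan says.** Section 2.3.1 holds the first stimulation session at the research centre to check tolerance and adds: "Subjects who cannot tolerate the study protocol will be dropped from the study". Section 7.2 places the session in Visit 1, after the questionnaires (HADS included) are listed, and counts it as treatment: "Subjects will have their first 1 hour treatment at OCNS (commencing Week 1 of the study". It continues: "Subjects who tolerate the device treatment will then have blood drawn for baseline biological measures". Men are then sent home with a device.

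Section 5.5 allocates by dispensing a coded kit ("50% of kits active, 50% sham") but does not say when. Section 4.4 keeps staff unaware of which devices are active and describes the sham: "In the sham devices, the electrodes attached to the device will be inactive". Section 9.2 starts safety recording at the same session: "AEs will be assessed from the first device treatment (screening visit) to the last device treatment".

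On follow-up, 5.6.2 provides an adverse event report for men who choose to withdraw and follow-up of adverse events, with no outcome assessment. Section 5.3 restricts the final visit to men who used the device on at least 5 of 7 days per week. Section 10.2 plans intention-to-treat and completer analyses for the behavioural measures, and analyses the biological measures only in men with pre- and post-treatment data. It defines neither the intention-to-treat set nor the handling of missing HADS scores.

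**The concern.** A tolerance check before randomisation only narrows the population. The same check after randomisation removes men from the comparison for a reason that treatment can cause. One such cause, a reaction to the current, exists only with an active kit. If the men removed would have improved less than those who stayed, the active mean is taken over a favourable subset and the HADS difference is too large.

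The visit is also labelled screening. Without a definition of when a man counts as randomised, a first-session failure could be classed as a screen failure and left out of the per-arm counts. No passage says that this is done, but none prevents it.

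**Working it through.** **Step 1: is the kit allocated before the session?** No sentence settles it. Pointing to yes:
- 7.2 calls the session the first treatment and starts Week 1 with it.
- 9.2 treats it as the first device treatment.
- 4.4 keeps staff blind to device type until data collection ends, so they have no described way to choose a known active device for a common trial run.
- No separate test device is described.

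Pointing the other way, 7.2 mentions a device going home only after the session and blood draw. Allocation first is therefore a strong inference, not stated text.

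**Step 2: what data does a dropped man have?**

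| Data | Available? | Source |
|---|---|---|
| Baseline HADS | Yes | 7.2 |
| Week 4 HADS | None planned after dropping | 2.3.1, 5.6.2 |
| Week 8 HADS | No; final visit needs device compliance | 5.3 |
| Baseline blood | No; drawn only after a tolerated session | 7.2 |

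He is absent from the completer and biological analyses, and enters an intention-to-treat analysis with a baseline score only.

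**Step 3: effect on the reported difference.** Section 13.3 gives mean decreases of 8.8 (active) and 3.64 (sham), so the difference is 8.8 − 3.64 = 5.16. Let q be the share of the active arm dropped for intolerance and m the mean decrease those men would have had. The mean over all allocated active men is (1 − q) × 8.8 + q × m, so the overstatement is q × (8.8 − m). The documents give no q. I assume 5% to 10%, with no matching loss in the sham arm.

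| Assumed m | q = 5% | q = 10% | Share of 5.16 |
|---|---|---|---|
| 8.8 (as other active men) | 0 | 0 | 0% |
| 3.64 (as sham) | 0.05 × 5.16 = 0.26 | 0.10 × 5.16 = 0.52 | 5% to 10% |
| 0 (no improvement) | 0.05 × 8.8 = 0.44 | 0.10 × 8.8 = 0.88 | 9% to 17% |

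With 13 active completers, this q means 13/0.95 − 13 = 0.7 to 13/0.90 − 13 = 1.4 men, or about one man.

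**Step 4: compared with the observed effect.** From t = 2.32 (sign dropped) with 13 and 11 men, the implied SD is 5.16 / (2.32 × √(1/13 + 1/11)) = 5.43, so d = 5.16/5.43 = 0.95. The largest overstatement above is 0.88/5.43 = 0.16 SD.

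**Step 5: error rate at the planned size.** Section 10.1 asks for 22 per group for 80% power at d = 0.80, one-sided 5%. By the noncentral t, 22 per group gives power 83.3%. The printed noncentrality (2.59) and 40 degrees of freedom belong to 21 per group, with power 81.7%. Either way 22 is sufficient. With no true effect, the completer bias is q × k SD, where k is how much worse, in SD, the dropped men would have done.

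| q | k | Bias (SD) | One-sided error, 22 per arm |
|---|---|---|---|
| any | 0 | 0 | 5.0% |
| 5% | 0.5 | 0.025 | 5.9% |
| 10% | 0.5 | 0.05 | 6.9% |
| 10% | 1 | 0.10 | 9.4% |

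**Step 6: price of keeping these men.** If they are retained and gain nothing, d becomes 0.80 × (1 − q). With 22 allocated per arm, power is 79.8% at q = 5% (d = 0.76) and 75.9% at q = 10% (d = 0.72).

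**The case against.** The strongest reply is that intention to treat is already planned for the primary outcome, that a mixed model is named in 10.2.1, and that HADS comes before the session, so nobody need be lost. This stands in part: loss of comparability is not automatic. But a man with only a baseline score carries no information on change. The model would in effect assume that he would have done as similar men who stayed in his arm did, which is exactly the point in doubt.

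Second, failures may be rare. Section 4.4 says "The current will not be detectable in both active and sham devices in order for adequate blinding to occur", 6.2.1 says "The dose selected is not detectable by the subject, so that adequate blinding can occur", and 2.3.1 links dizziness and headache mainly to higher current. That stands, subject to a conflict: 6.2.1 gives 100 microamperes while 6.2 also allows up to 600, and these passages must be reconciled.

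A reader might go further in four ways that the documents do not support:
- That only active-arm men can fail. Section 2.3.1 also lists skin irritation, sham men wear the same clips, and a headache can be coincidental.
- That sham men might receive an hour of active stimulation from a common device and learn to recognise it. No such device is described, staff are blind to device type, and the current is said to be undetectable.
- That intolerance vanishes from the safety record. Section 9.2 records adverse events from this very session. What is missing is a count of first-session drops by arm.
- That excess loss occurred in the active arm. Section 13.2 reports 13 active and 11 sham completers, which does not suggest it. It does not exclude it either, because the readable text gives no numbers allocated per arm; a figure at that point is not shown and may contain them.

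**Conclusion.** The point holds conditionally. The plan drops men who fail the first session, and it plans no later HADS for them. If the kit is allocated beforehand, as the text suggests without saying so, this is a post-randomisation exclusion that can differ by arm, and the named intention-to-treat analysis cannot correct it with the data planned.

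The size is unknown and may be zero. At an assumed active-arm failure rate of 5% to 10%, the overstatement runs from 0 to 0.88 of 5.16 points, depending on how the dropped men would have fared. Any matching sham failures could reduce it. A reader might infer that the arms were shown to be non-comparable, or that the reported benefit is an artefact. Neither follows: no such drop is documented, and even the largest value in this range leaves most of the observed difference. This is an inexpensive safeguard worth adding, not a demonstrated bias.

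**What to change.** - **5.5 and 7.2:** state that all other eligibility criteria are confirmed before a kit is allocated, that a man is randomised at the moment of allocation, and that the first session uses that kit.
- **2.3.1:** replace the rule removing intolerant men from the study. A man who stops the device for intolerance stays in the intention-to-treat set in his allocated arm, is not counted as a screen failure, and is asked for HADS at weeks 4 and 8. Whether he stops the device is unchanged.
- **5.3:** align the final-visit rule so that he can give the week 8 HADS.
- **10.2:** define the intention-to-treat set as all randomised men.
- **Reporting:** give numbers allocated and first-session intolerance by arm. Results are already written up in section 13, so this part is useful now; the actual counts can replace the assumed 5% to 10% in the calculation above.
- **6.2 and 6.2.1:** reconcile the two current levels.

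The cost is a few sentences and two questionnaire contacts for a few men. The estimate may be slightly less favourable, with the modest fall in power shown in step 6 if the retained men gain nothing.

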2.3.2 Potential Benefits

This study may improve emotional well-being for individual subjects with proper and consecutive use of the CES device but any beneficial effects are not certain to occur. It is hoped that the research will also benefit Veterans and individuals suffering with anxiety and/or depression by increasing awareness of these conditions and further research to identify improved diagnostic markers for anxiety and depression. Societal benefits of this study include the potential addition of a non-invasive, non-medication treatment options for patients with anxiety and/or depression. Cellular marker identification and an improved understanding of the physiological mechanisms behind CES therapies may enhance and improve therapies currently available.

3 OBJECTIVES

3.1 Study Objectives

We anticipate significant improvements in emotional well-being associated with eight-weeks of daily CES treatment. Scores on the individual and combined anxiety and depression subscales of the HADS will decrease. Improvements in other aspects of mental health (measured with the MHC-SF) are expected as a secondary effect of the improved negative affect measured in the HADS. An increase in telomerase is expected at 8 weeks. In addition we expect improvements in the PROMIS measures of fatigue, sleep disturbance, and pain interference.

Biological samples will be retained for measurement of additional inflammatory gene regulation pathways in peripheral immune cells if additional funding can be obtained for processing and analysis of the samples. We anticipate that inflammatory gene profiles would be improved in subjects who have improved emotional wellbeing with CES treatment.

